5. STATISTICAL ANALYSES

5.1. General Considerations

Unless specified otherwise, efficacy data summaries will be provided by intervention group for the FAS for 77242113PSO2001 and 77242113PSO2002 respectively defined in [Section 4.1](#) and [Section 4.2](#). Data primarily will be summarized using descriptive statistics. Continuous variables will be summarized using the number of observations, mean, SD, median, interquartile range, minimum and maximum, as appropriate. Categorical values will be summarized using the number

of observations and percentages as appropriate. In addition, graphical data displays (eg, line plots) and participant listings may also be used to summarize/present the data.

Study 77242113PSO2001

CCI

In addition, for binary response efficacy endpoints, comparisons between each of the JNJ-77242113 groups versus placebo will be performed using a Cochran-Mantel-Haenszel (CMH) test stratified by the baseline weight (≤ 90 kg, > 90 kg). For continuous efficacy endpoints, treatment comparisons will be performed using a Mixed-Effect Model Repeated Measure (MMRM) model. The MMRM model will have treatment group, baseline weight (≤ 90 kg, > 90 kg), and baseline value for the corresponding efficacy endpoint as explanatory factors. The MMRM model will also include visit, treatment group by visit interaction, baseline weight (≤ 90 kg, > 90 kg) by visit interaction, and baseline value by visit interaction as additional explanatory factors. The Least Square mean (LSmean) estimates and their corresponding 95% confidence interval (CI) will be provided at each time point. In addition, the estimates of LSmean difference and 95% CIs between the JNJ-77242113 groups and placebo will be provided.

In general, all statistical tests will be performed at a 2-sided significance level of $\alpha=0.05$. No multiplicity adjustment will be made for the secondary endpoints being tested and nominal p-values will be reported.

The baseline measurement is defined as the closest measurement taken prior to or at the time of the first study agent administration date unless otherwise specified.

Study 77242113PSO2002

Study 77242113PSO2002 is the LTE study of the originating study 77242113PSO2001 and no formal hypothesis testing will be performed for the primary and secondary endpoints. The baseline data from the originating study (77242113PSO2001) will be used to calculate the change-from-baseline-related endpoints.

5.1.1. Visit Windows

The schedules for visits of the study will follow per protocol ‘Schedule of Activities’ table. Nominal visits will be used for all by-visit analyses in the study.

- 77242113PSO2001: Visits at Week 1 and Week 2 should occur within ± 2 days of the scheduled visit; and the visits after Week 2 though Week 16 should occur within ± 4 days of the scheduled visit.

- 77242113PSO2002: the visits through Week 36 should occur within ± 4 days of the scheduled visit.

5.1.2. Reference Date, Study Day and Relative Day

Study 77242113PSO2001

The Reference Date is the date of the first study agent administration in study 77242113PSO2001. If the date of the first study agent administration is missing or the first study agent administration is not done, then the Reference Date equals the corresponding visit date (eg, Week 0 visit date). If the corresponding visit date is also missing, then the Reference Date equals the randomization date. Study day is defined as the number of days from the study reference date to the event/visit date. It will be calculated as follows:

- If the event/assessment occurs on or after the reference date, then study day = event/assessment date – reference date + 1.
- If the event/assessment occurs before the reference date, then study day = event/assessment date – reference date.

Hence, the day of reference date is Study Day 1; the previous day is Study Day -1.

Study 77242113PSO2002

For summaries based on the combined data from studies 77242113PSO2001 and 77242113PSO2002 (eg, safety through Week 56 [Week 40 of the 77242113PSO2002 study]), the reference date of the study 77242113PSO2001 defined above will be used. Same calculation algorithm to calculate the study day specified above for study 77242113PSO2001 will be applied.

For summaries based on data from 77242113PSO2002 only (eg, safety from Week 0 through Week 40 of the 77242113PSO2002 study) the reference date is the date of the enrollment in study 77242113PSO2002. If the enrollment date is missing then the Reference Date equals the corresponding visit date (eg, Week 0 visit date of 77242113PSO2002). If the corresponding visit date is also missing, then the Reference Date equals the estimated Week 16 visit date of the participant in study 77242113PSO2001. Same calculation algorithm to calculate the study day specified above for study 77242113PSO2001 will be applied.

5.1.3. Treatment Groups

5.1.3.1. Study 77242113PSO2001

In the efficacy analyses, FAS (Section 4.1) will be used and the participants will be analyzed according to the randomized treatment groups they were assigned to, regardless of the treatments they actually received. Unless otherwise specified, efficacy analyses for placebo comparisons at Week 16 or through Week 16 will be summarized and displayed as follows:

- **Placebo:** Participants randomized to placebo group at Week 0.
- **JNJ-77242113 25 mg QD:** Participants randomized to 25 mg QD group at Week 0.
- **JNJ-77242113 50 mg QD:** Participants randomized to 50 mg QD group at Week 0.
- **JNJ-77242113 25 mg BID:** Participants randomized to 25 mg BID at Week 0.
- **JNJ-77242113 100 mg QD:** Participants randomized to 100 mg QD at Week 0.
- **JNJ-77242113 100 mg BID:** Participants randomized to 100 mg BID at Week 0.

5.1.3.2. Study 77242113PSO2002

Efficacy summaries for 77242113PSO2002 study will be based on the pooled data from both 77242113PSO2001 and 77242113PSO2002 studies, FAS (Section 4.2) will be used and participants will be summarized and presented by randomized treatment group at Week 0 of 77242113PSO2001 study:

- **Placebo→: JNJ-77242113 100 mg QD:** Participants randomized to placebo group at Week 0.
 - Only participants crossed over to receive JNJ-77242113 100 mg QD at Week 16 will be included in the summary for the visits after Week 16.
- **JNJ-77242113 25 mg QD:** Participants randomized to 25 mg QD group at Week 0.
- **JNJ-77242113 50 mg QD:** Participants randomized to 50 mg QD group at Week 0.
- **JNJ-77242113 25 mg BID:** Participants randomized to 25 mg BID at Week 0.
- **JNJ-77242113 100 mg QD:** Participants randomized to 100 mg QD at Week 0.
- **JNJ-77242113 100 mg BID:** Participants randomized to 100 mg BID at Week 0.

For the efficacy overtime analyses that combines the 77242113PSO2001 and 77242113PSO2002 studies, Week 4 visit of the study 77242113PSO2002 will be aligned as Week 20 for the combined study and will be denoted as “Week 20 (LTE Week 4)” in the summary table; similar notation will be applied for the subsequent visits of the study 77242113PSO2002.

5.2. Participant Dispositions

The number of screened participants will be summarized overall.

The number of participants in the following disposition categories will be summarized throughout the study by intervention group and overall:

- Participants randomized
- Participants who received study intervention
- Participants who completed the study
- Participants who discontinued study intervention
 - Reasons for discontinuation of study intervention

- Participants who terminated study prematurely
 - Reasons for termination of study

Listings of participants will be provided for the following categories:

- Participants who discontinued study intervention
- Participants who terminated study prematurely
- Participants who were unblinded during the study period
- Participants who were randomized yet did not receive study intervention

The above categories will include summaries over the placebo-controlled period (through Week 16) for study 77242113PSO2001 and through Week 52 for the combined study 77242113PSO2001 and study 77242113PSO2002.

In addition, a listing of participants who were randomized with incorrect stratum and a listing of participants who did not enter to 77242113PSO2002 study will be provided for 77242113PSO2001 study.

5.3. Primary Endpoint Analysis

5.3.1. Study 77242113PSO2001

5.3.1.1. Definition of Primary Endpoints

The primary efficacy endpoint is the proportion of participants achieving PASI 75 response at Week 16, defined as at least a 75% reduction from baseline in PASI total score.

The PASI is a system used for assessing and grading the severity of psoriatic lesions and their response to therapy. In the PASI system, the body is divided into 4 regions: the head, trunk, upper extremities, and lower extremities which account for 10%, 30%, 20%, and 40% of the total BSA, respectively. Each of these areas is assessed separately for erythema, induration, and scaling, which are each rated on a scale of 0 to 4; and the area of involvement for psoriatic lesion is rated on a scale of 0 (no involvement) to 6 (90% to 100% involvement). The PASI produces a numeric score that can range from 0 (no psoriasis) to 72. A higher score indicates more severe disease.

Efficacy endpoints related to the PASI score are defined below:

PASI 50 Responders

Participants with $\geq 50\%$ improvement in PASI from baseline will be considered PASI 50 responders.

PASI 75 Responders

Participants with $\geq 75\%$ improvement in PASI from baseline will be considered PASI 75 responders.

PASI 90 Responders

Participants with $\geq 90\%$ improvement in PASI from baseline will be considered PASI 90 responders.

PASI 100 Responders

Participants with a PASI score of 0 will be considered PASI 100 responders.

5.3.1.2. Estimands

Primary Trial Objective: To evaluate the dose response of JNJ-77242113 at Week 16 in participants with moderate-to-severe plaque psoriasis.

Estimand Scientific Question of Interest: What is the proportion of participants considered to have benefited from JNJ-77242113 versus placebo assessed by the PASI75 response at Week 16?

5.3.1.2.1. Primary Estimand (Estimand 1)

The primary estimand, based on the above primary objective, is defined by the following 5 attributes which assess the treatment effects not only based on the variable measurements, but also based on intercurrent events:

Study intervention:

- JNJ77242113 25 mg QD, 50 mg QD, 25 mg BID, 100 mg QD, and 100 mg BID.
- Placebo

Population: adult participants with moderate to severe psoriasis

Variable/endpoint: Binary response variable, where a responder is defined as a participant achieving a PASI75 response at Week 16. A participant with an intercurrent event in categories 1-2 defined below will be considered as a non-responder.

Intercurrent Events (ICEs) and their corresponding strategies.

ICEs	Analysis Strategy for Addressing Intercurrent Events
1. Discontinuation of study intervention due to lack of efficacy, or an AE of worsening of psoriasis prior to Week 16	Composite Strategy: Participants with these intercurrent event are considered as non-responders. The occurrence of these intercurrent events is captured in the variable definition.

2. Initiation of a protocol-prohibited medication or therapy during the study that could improve psoriasis prior to Week 16	
3. Discontinuation of study intervention for reasons other than ICE 1	Treatment Policy: observed data will be used regardless of whether or not this intercurrent event had occurred.

- ICEs 1 and 2 will be handled by the composite strategy, where the occurrence of the ICE will be incorporated into the variable definition. Participants experiencing ICE 1 or 2 will be considered not to have achieved the primary endpoint.

- ICE 3 will be handled using the treatment policy strategy regardless of the intercurrent event.

Note: For participants experiencing multiple ICEs, ICE 2 will override ICE 3.

A list of Participants who experienced ICEs 1-3 will be provided.

Population level summary: Difference in the proportions of participants achieving a PASI 75 responses at Week 16 between the treatment groups.

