9.4.2.1.1. Estimand

9.4.2.1.1.1. Primary Estimand

The primary estimand (ie, a precise definition of the primary targeted treatment effect) is defined by the following 5 attributes:

Study intervention:

- JNJ-77242113 25 mg QD, 50 mg QD, 25 mg BID, 100 mg QD, and 100 mg BID
- Placebo

Population: adult participants with moderate to severe plaque psoriasis

Variable/endpoint: Response binary variable, where a responder is defined as a participant achieving a PASI 75 response at Week 16 who does not have intercurrent events in categories 1-2 (defined below).

Intercurrent Events (ICEs) and their corresponding strategies

ICEs	Analysis Strategy for Addressing Intercurrent Events
1. Discontinuation of study intervention due to lack of efficacy or due to an AE of worsening of psoriasis	Composite Strategy: Participants with these intercurrent events are considered as PASI 75 non-responders after these events, and prior to Week 16. The occurrence of these intercurrent events is captured in the variable definition.

2. Initiation of a protocol-prohibited medication or therapy during the study that could improve psoriasis	
3. Discontinuation of study intervention for reasons other than ICE 1	Treatment Policy: observed data will be used regardless of whether or not this intercurrent event had occurred.

Note: For participants experiencing multiple ICEs, ICE 2 will override ICE 3.

Population level summary: Difference in the proportions of participants achieving a PASI 75 response at Week 16 between the JNJ-77242113 and placebo intervention groups.

Primary Endpoint Analysis

In the primary efficacy analysis, data from all randomized participants who received at least 1 administration of study intervention will be analyzed according to their assigned treatment group.

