4. POPULATIONS (ANALYSIS SETS) FOR ANALYSIS

Unless specified otherwise, data included in the analyses for both studies are briefly summarized below:

4.1. 77242113PSO2001

All data available through Week 16 database lock of the 77242113PSO2001 study will be included. The populations for analysis are defined in [Table 3](#) below.

Table 3: Populations for Analyses for 77242113PSO2001

Population	Description
Enrolled	All participants who signed the ICF
Randomized	All participants who were randomized in the study
FAS	All randomized participants who took at least 1 dose of study intervention
Per Protocol (PP)	The per protocol analysis set (PP) includes a subset of participants in the full analysis set (FAS) who were in compliance with the protocol. Compliance is defined as participants in FAS and meet the following criteria: 
 • Has a total BSA $\geq 10\%$ at the screening and baseline visit. • Has a total PASI score ≥ 12 at the screening and baseline visit • Has a total IGA score ≥ 3 at the screening and baseline visit • Received all scheduled treatment and with overall compliance of study treatment at least 80% prior to Week 16, Or participants who did not complete all scheduled study intervention administration due to intercurrent events (i.e., discontinued the study intervention due to lack of efficacy, an AE of worsening of psoriasis, or started a protocol-prohibited medication or therapy during the study that could improve psoriasis)
Safety Analysis Set	All randomized participants who took at least 1 dose of study intervention
PK Analysis Set	All randomized participants who received at least 1 complete dose of JNJ-77242113 and had at least 1 valid blood sample drawn for PK analysis after their first dose of JNJ-77242113
Immunogenicity Analysis Set	All randomized participants who received at least 1 dose of JNJ-77242113 and who had at least 1 sample obtained after the first dose of JNJ-77242113 for the detection of antibodies to JNJ-77242113
PD Analysis Set	All randomized participants who received at least 1 complete dose of JNJ-77242113

4.2. 77242113PSO2002

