5.3.1.2.3. Analysis Methods for the Primary Estimand

The primary endpoint will be analyzed based on the primary estimand (Section 5.3.1.2.1) and the data from all participants in FAS (Section 4.1) will include data from all randomized participants who received at least one administration of study intervention based on their assigned intervention group, regardless of the actual intervention received.

Participants with ICEs 1-2 before Week 16 will be considered as PASI75 non-responders at Week 16. Participants with ICE 3, observed PASI data after this ICE will be utilized in the analysis. After accounting for the ICEs for the primary estimand, participants with the missing data of the primary endpoint at Week 16 will be considered as non-responders.

The MCP-Mod will be used to test if there is a positive overall treatment effect based on candidate dose-response models. For each candidate model a contrast test statistic, based on a linear combination of the treatment estimates per dose will be derived. The contrast coefficients will be chosen to maximize the power to detect the pre-specified candidate models. The global test decision is based on the maximum of the contrast test statistics. The overall positive dose-response will be tested at a 2-sided 5% significance level. This procedure takes into account the multiplicity arising from testing several models and thus preserving the family wise Type I error rate.

CCI

Generalized Multiple Comparison Modelling (gMCP-Mod)

To demonstrate the dose-response relationship across JNJ-77242113 treatment groups and placebo for the primary endpoint, the primary analysis will be based on a generalized Multiple Comparisons and Modeling (gMCP-Mod) analysis^{1,2}. This analysis tests for a dose-response relationship, allowing for uncertainty in the dose-response relationship through inclusion of contrasts from multiple pre-specified candidate models to assess dose-response. If a dose-response relationship exists, then fitted estimates for the incidence of the primary endpoint will be calculated in each of the treatment groups using the selected dose-response models.

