6.4. Appendix 4 Protocol Deviations

In general, the following list of major protocol deviations may have the potential to impact participants' rights, safety or well-being, or the integrity and/or result of the clinical study. Participants with major protocol deviations will be identified prior to database lock and the participants with major protocol deviations will be summarized by category through Week 16 and through the end of study.

- Developed withdrawal criteria but not withdrawn
- Entered but did not satisfy criteria
- Received a disallowed concomitant treatment
- Received wrong treatment or incorrect dose
- Other

A listing of participants with major protocol deviations will also be provided by randomized treatment group. In addition, analyses of COVID-19 related protocol deviations will be provided.

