6.5. Appendix 5 Prior and Concomitant Medications

Prior medications are defined as any therapy used before the day of first dose (partial or complete) of study intervention. Previous psoriasis medications/therapy will be summarized by intervention group.

Concomitant medications will be coded using the World Health Organization Drug Dictionary (WHO-DD). Concomitant medications are defined as any therapy used on or after the same day as the first dose of study intervention, including those that started before and continue on after the first dose of study intervention.

Summaries of concomitant medications will be presented by anatomic and therapeutic class (ATC) term, and intervention group. The proportion of participants who receive each concomitant medication will be summarized as well as the proportion of participants who receive at least 1 concomitant medication.

Participants' psoriasis medication history with topical agents, phototherapy, non-biologic systemic therapies, and biologic medications will be summarized by treatment group for all randomized participants. If data are available, total cumulative duration of treatment with these medications will be summarized. In addition, reasons for which participants discontinued previous systemic therapies (contraindication, inadequate response, intolerance [ie, AEs], or other) will be summarized by randomized treatment group.

The number of participants who received concomitant treatment of moisturizer for psoriasis will be summarized by randomized treatment group.

Participants who received concomitant corticosteroids for indications other than psoriasis and/or psoriatic arthritis will be listed. Participants with concomitant prophylactic treatments for latent TB infection will also be listed.

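### ICE 2 counts only newly started prohibited therapy, and the per-protocol set does not screen for washout breaches, so a tolerated carried-over therapy could count as PASI 75 response in both analyses (minor)

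*SAP*

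**What the plan says.** SAP 5.3.1.2.1 defines ICE 2 as "Initiation of a protocol-prohibited medication or therapy during the study that could improve psoriasis prior to Week 16". The protocol's primary estimand (9.4.2.1.1.1) has the same trigger: "Initiation of a protocol-prohibited medication or therapy during the study that could improve psoriasis". SAP 5.3.1.2.3 gives the consequence: "Participants with ICEs 1-2 before Week 16 will be considered as PASI75 non-responders at Week 16". Stopping study drug for other reasons (ICE 3) follows treatment policy: "Participants with ICE 3, observed PASI data after this ICE will be utilized in the analysis".

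Other sections use wider terms. Protocol 6.8 addresses prohibited therapy that is administered between Week 0 and Week 16. SAP Appendix 5 counts as concomitant all therapies used from the day of first dose, "including those that started before and continue on after the first dose of study intervention".

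The per-protocol set in SAP Table 3 is a fixed list within the full analysis set. It requires the entry thresholds for BSA, PASI and IGA at screening and baseline, and "Received all scheduled treatment and with overall compliance of study treatment at least 80% prior to Week 16". Participants who did not complete treatment because of ICE 1 or 2 are kept. SAP 5.3.1.2.6 applies the primary estimand to this set, except that participants with ICE 3 who did not complete treatment before Week 16 are removed.

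SAP Appendix 4 lists major deviations, to be identified before database lock. They include entering without meeting the criteria, "Received a disallowed concomitant treatment" and "Received wrong treatment or incorrect dose". These are summarised and listed. No rule ties them to responder status or to per-protocol membership.

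**The concern.** The composite strategy exists so that improvement helped by another psoriasis therapy is not credited to the assigned arm. Its trigger is the act of starting such a therapy. A participant who was already on one at first dose and stayed on it has started nothing, so the Week 16 PASI is used as observed.

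The per-protocol analysis is where one would expect this case to be removed. It repeats three eligibility checks but not the timed prior-therapy criteria (Exclusions 4–9, 12 and 13 in Protocol 5.2), although Exclusions 12 and 13 concern therapies that can distort PASI. The hypothetical supplementary estimand (SAP 5.3.1.2.2.1) discards data only after ICEs 1–3, and the secondary endpoints reuse the same events (SAP 5.4.1.2.2). Agreement among these analyses would therefore say nothing about carried-over therapy.

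**Working it through.** This is mainly a comparison of texts; the arithmetic only sets the scale.

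**Step 1: follow each case through the rules.**

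| Case | ICE 2? | Primary analysis | Per-protocol analysis |
|---|---|---|---|
| Prohibited therapy started after first dose | Yes | Non-responder | Non-responder |
| Started in screening, continued | Arguably yes: Protocol 4.1 counts screening within the study's duration | Non-responder on that reading | Same |
| Started before screening, continued, not withdrawn | No | Observed PASI | Kept if thresholds and compliance are met; observed PASI |
| Washout breached, therapy stopped before first dose | No | Observed PASI | Kept; observed PASI |
| Wrong kit received | No | Observed PASI, as randomised | Unclear: depends on how receipt of all scheduled treatment is read |

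The third row is the gap. In the fourth row, a residual effect would lower baseline PASI and then wane, which tends to work against response. On the fifth row, SAP Appendix 7 defines percent compliance by tablet count. It also summarises deviations for an incorrect agent or dose, but attaches no exclusion rule to them.

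**Step 2: reproduce the plan's pairwise power.** Inputs from SAP 3.1: n = 40 per arm, two-sided alpha 0.05, placebo rate 5% to 10%, difference 35 points. With p̄ the mean of the two rates, the pooled two-sample Z-test gives

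power = Φ{[d − 1.96·√(2p̄(1−p̄)/n)] / √[(p₁(1−p₁) + p₂(1−p₂))/n]}.

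- 5% vs 40%: (0.35 − 0.1830)/0.0848 = 1.97, power 97.6%.
- 10% vs 45%: (0.35 − 0.1957)/0.0919 = 1.68, power 95.4%.

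Both satisfy the stated minimum of 90%.

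**Step 3: size per participant.** One responder in 40 is 1/40 = 2.5 points. The assumed placebo rate of 6% is 0.06 × 40 = 2.4 responders. A chance imbalance of two such responders between two arms shifts their difference by up to 2/40 = 5 points.

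**Step 4: illustration under assumptions that are not in the documents.** Let a share f of every arm be on carried-over therapy, and let it turn a share q of would-be non-responders into responders. Each rate becomes p + f·q·(1 − p) under the present wording, and p·(1 − f) if all such participants are set to non-response.

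| Base rates | f, q | As written: rates, difference, power | Set to non-response: rates, difference, power |
|---|---|---|---|
| 5% vs 40% | 5%, 0.5 | 7.4% vs 41.5%, 34.1 points, 95.9% | 4.75% vs 38.0%, 33.3 points, 96.6% |
| 5% vs 40% | 10%, 0.75 | 12.1% vs 44.5%, 32.4 points, 91.0% | 4.5% vs 36.0%, 31.5 points, 95.4% |
| 10% vs 45% | 10%, 0.75 | 16.8% vs 49.1%, 32.4 points, 88.4% | 9.0% vs 40.5%, 31.5 points, 91.9% |

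With equal shares across arms the effect is modest dilution. Of these three scenarios, only the most extreme takes power below 90%. Setting these participants to non-response does not restore a 35-point difference; the gain is that the estimand treats assisted response consistently.

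**The case against.** The case against giving this much weight is strong, and most of it stands.

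- **Conduct rules narrow the route.** Eligibility is re-checked before first dose and waivers are barred (Protocol 1.3 and 5). Under 6.8 a participant given prohibited therapy may be taken off study treatment, and 7.2 provides for withdrawal for breaching prohibitions. A withdrawn participant without a Week 16 PASI is a non-responder, and one who stops study drug early for a reason other than ICE 1 or 2 leaves the per-protocol set. The gap therefore needs a breach that is detected and tolerated. It is not closed entirely: discontinuation under 6.8 is at the medical monitor's discretion, and 7.1 also speaks of initiation. An undetected breach would escape the fix as well.
- **Baseline absorbs stable therapy.** PASI must be at least 12 at screening and baseline, and change is measured from the last value at or before first dose (SAP 5.1). The residual risk is a therapy begun shortly before screening and still gaining effect.
- **The per-protocol analysis is secondary.** It covers pairwise comparisons only, while the study is judged on the dose-response test.

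A reader might infer more than the documents support:

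- That anyone who starts therapy shortly before Week 0 escapes ICE 2. Protocol 4.1 places screening inside the study, so this is at best arguable.
- That the per-protocol analysis ignores disallowed therapy altogether. It still applies ICE 2 to newly started therapy.
- That a participant given the wrong kit certainly stays in the per-protocol set. The requirement to have received all scheduled treatment may already exclude that person; the text is unclear.
- That the primary result is biased towards the drug. Randomisation and blinding make a systematic imbalance between arms unlikely.

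**Conclusion.** The definitional gap is real and narrow. As written, a participant who began a prohibited psoriasis therapy before screening, continued it past first dose and was allowed to stay on study drug can be a PASI 75 responder in both the primary and the per-protocol analyses.

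Each such responder is worth 2.5 points in an arm of 40. The documents give no deviation rate. If, purely by assumption, 1% to 3% of 240 had a relevant deviation, that is 2.4 to 7.2 people, or 0.4 to 1.2 per arm, and only some of them would respond because of the other therapy. The expected effect is small, and nothing here suggests that the dose-response conclusion would change. This is a cheap improvement of minor severity: it makes the per-protocol check more informative and settles the handling before unblinding.

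**What to change.** 1. **Per-protocol set (SAP Table 3).** Exclude participants with an Appendix 4 major deviation, identified before lock, for any of the following: a breached washout criterion for a therapy that could affect psoriasis (among Exclusions 4–9, 12 and 13); disallowed psoriasis therapy not already counted as ICE 2; or wrong treatment received. The last item makes explicit what the treatment-receipt criterion may already imply. Exclusion 3 is a lifetime bar rather than a washout, so it need not be on the list.
2. **ICE 2.** Define it as use, whether initiated or continued, on or after first dose and before Week 16, of a protocol-prohibited therapy that could improve psoriasis. The protocol's primary estimand has the same trigger, so either align it there or record the change in SAP Appendix 2, which at present lists none.

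Both parts are needed. The ICE 2 wording handles continued therapy; the per-protocol rule handles washout breaches where the therapy has stopped.

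No new data are required, because concomitant medications and major deviations are already recorded. The cost is the wording, one protocol alignment or logged change, and a few participants lost from the per-protocol set. The new ICE 2 would also count some long-stable users as non-responders.
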